 - Blood samples for PTC857, riluzole, edaravone, and/or sodium phenylbutyrate/taurursodiol PK will be collected from those subjects taking part in the PK Sub-Study at predose (prior to the first dose of the day) and at 1, 2, 4, 5, 6, 8, and 12 hours (±15 minutes) (prior to the second dose) post-dose on Day 1 and Day 29. Blood samples for PTC857 PK only will be collected predose (prior to the first dose of the day) and at 1 hour (±15 minutes) and 4 hours (±1 hour) post-dose on Day 85, and predose only at all subsequent visits with blood PK sampling. Subjects should be instructed not to take riluzole, edaravone, and/or sodium phenylbutyrate/taurursodiol on Day 1 or Day 29 prior to the study visit. Time of last dose of study drug and riluzole, edaravone, and/or sodium phenylbutyrate/taurursodiol prior to the study visit should be recorded.
 - Additional samples of predose (trough) CSF will be collected for PK evaluation at all lumbar puncture timepoints.
 - Additional ECG measurements will be performed at the time of the 4-hour and 8-hour post-dose PK samples (±15 minutes from PK sample blood draw).
- ² The lumbar punctures for CSF collection in the PK Sub-Study may occur within 5 days prior to or after the scheduled visit day.

Table 2: Schedule of Assessments for the Long-Term Extension Period (Part B)

| | | EOS/ Follow-Up | Early Termination | | | | | |
|--|-----------------|--------------------|----------------------|--------------------|-----------------|--------------------|------------------|----------------|
| Study Day | Day 169 (±3) | Day 183 (±3) | Day 197 (±3) | Day 225 (±3) | Day 253 (±3) | Day 365 (±5) | Day 393 (±3)ª | ET⁵ |
| | | | | | | End of Treatment c | | |
| Telephone call/in-home or in-person visit ^d | IP | PC/IH ^d | PC/IH ^d | PC/IH ^d | IP | IP | PC | IP |
| Informed consent | Xe | | | | Xf | Xg | | |
| Weight and BMI | | | | | Х | X | | Х |
| Serum/urine pregnancy test (female subjects only) ^h | | | (Monthly | / [Days 197, 225 | , 253, 281, 309 | , 337, and 365]) | X | X |
| 12-Lead ECG ⁱ | | | , , | | X | X | | Х |
| Vital signs ^j | | | Х | Х | Х | Х | | Х |
| Physical exam ^k | | | | | Х | Х | | Х |
| PK blood sample | | | | | Х | X | | Х |
| Clinical laboratory tests ^m | | Xn | Х | Х | Х | X | | Х |
| Laboratory biomarkers (blood and urine)° | | | | | Х | X | | Х |
| ALSFRS-R ^p | | | Х | Х | Х | Х | Х | Х |
| PFTs ^q | | | | | Х | X | | Х |
| ALS CBS | | | | | Х | Х | | Х |
| Modified Norris Scale | | | | | Х | X | | Х |
| ALSAQ-40 | | | | | Х | X | | Х |
| EQ-5D-5L | | | | | Х | Х | | Х |
| C-SSRS ^r | | | X | Х | Х | Х | X | Х |
| Study drug dispensation | X | | | | Х | | | |
| Adverse events | | Χ | X | X | X | X | X | X |
| Prior/concomitant medications | | Χ | X | X | X | X | X | X |
| Mammogram ^s | X | | | | | X | | X ^t |

Abbreviations: ALS, amyotrophic lateral sclerosis; ALS CBS, ALS Cognitive Behavioral Screen; ALSAQ-40, ALS Assessment Questionnaire; ALSFRS-R, ALS Functional Rating Scale-Revised; BMI, body mass index; CAFS, Combined Assessment of Function and Survival; CSF, cerebrospinal fluid; C-SSRS, Columbia-Suicide Severity Rating Scale; ECG, electrocardiogram; EOS, end of study; EQ-5D-5L, five-level European quality of life five-dimensional questionnaire; ET early termination; ICF, Informed Consent Form; IH, in-home; IP, In-person; LTE, Long-Term Extension; PC, telephone call; PFT, pulmonary function test; PI, Principal Investigator; PK, pharmacokinetic

^a Follow-up Visit on Day 393 only for subjects who choose not to enter the Continued LTE Period (Part C).

^b For subjects who early terminate from the study and consent to continued follow-up, the investigator should attempt to gain vital status on the participant and conduct the ALSFRS-R assessment approximately every 28 days for the remaining duration of the study, in accordance with local requirements/regulations.

Day 365 will be considered the End of Treatment Visit only for those who choose not to enter the Continued LTE Period (Part C).

^d For the telephone call/in-home visit, where applicable, the ALSFRS-R, C-SSRS, adverse events, and prior/concomitant medications assessments will be conducted via a telephone call. Vital signs assessments and samples for clinical laboratory tests will be collected via a home health nurse during applicable inhome visits at the subject's home during these visits. Subjects may go to the site for an in-person visit at the discretion of the PI. Visits indicated as in-person only may be conducted remotely (ie, in-home) following discussion between the site and the medical monitor. In-person visits that are conducted remotely must include the following assessments, at minimum (if such assessments are typically included during the visit): serum/urine pregnancy test (females only), vital signs, clinical laboratory tests, ALSFRS-R, C-SSRS, adverse events, prior/concomitant medications, sparse PK blood sampling, laboratory biomarkers, and ALSAQ-40.

e Subjects who decide to enter the LTE Period should sign the consent form before the start of the LTE Period.

- The ICF for Part C should be provided to the subject at the Day 253 visit to allow the subject adequate time to consider transitioning into Part C.
- ⁹ The ICF for Part C should be signed by the subject at the Day 365 visit if they choose to enroll into Part C.
- h Women of childbearing potential will undergo monthly urine pregnancy testing on Days 197, 225, 253, 281, 309, 337, and 365, and at the Follow-up Visit. If a urine pregnancy test is positive, a serum pregnancy test will be conducted for confirmation and dosing should be immediately suspended and evaluated for continued study participation based upon the result of the serum pregnancy test and in discussion with the medical monitor. For months where an on-site visit is not scheduled, subjects will complete a urine pregnancy test at home, if local requirements allow, to be reported to the investigator and documented in the eCRF. Single 12-lead ECG measurements will always be performed prior to the dose of medication administered at the clinic. Subjects should be resting for at least 5 minutes in supine position prior to 12-lead ECG procedures.
- J Vital signs will consist of measurements of supine blood pressure, heart rate, body temperature, and respiratory rate. Vital sign measurements will be collected after the subject has been resting for 5 minutes. Blood pressure and heart rate measurements will be performed with subjects in a supine position, except when they semi reclined because of study procedures and/or AEs (eg, nausea, dizziness) or if deemed necessary by the PI or designee.
- ^k A targeted physical examination, including neurological examination, will be completed at all timepoints.
- Blood samples for PK evaluation will be collected from all subjects at predose only.
- ^m Clinical laboratory tests will consist of fasting lipid profile, hematology, coagulation, blood chemistry, and urinalysis. Urinalysis will only be performed at in-person clinic visits (ie, Day 253 and Day 365).
- ⁿ Clinical laboratory tests on Day 183 will consist only of a fasting lipid profile. Hematology and blood chemistry will not be evaluated during this visit.
- ^o Laboratory (blood and urine) biomarkers (aligned with the timing for the clinical laboratory tests) as per Section 7.1.7. Urine creatinine should be tested when urine p75NTR is sampled.
- ^p The ALSFRS-R assessment must be performed by a certified rater.
- ^q Pulmonary function tests will assess slow vital capacity and Sniff Nasal Inspiratory Pressure. Forced vital capacity, vital capacity, forced expiratory volume, and maximum inspiratory pressure will not be measured. Oxygen saturation, respiratory rate, and heart rate will be assessed in both upright and supine positions. The Sniff Nasal Inspiratory Pressure test will assess nasal pressure in each unilaterally occluded nostril during a maximal sniff to assess inspiratory muscle strength.

 ^r At all visits, the Since Last Visits C-SSRS will be administered.
- s Mammograms to be conducted for female subjects only. If clinically indicated, an ultrasound or MRI may also be conducted for breast cancer imaging, per the investigator's discretion.
- ^t Women who have been exposed to study drug for at least 3 months and discontinue treatment before reaching the Day 365 Visit will have breast cancer surveillance imaging performed at the Early Termination Visit. Women who have been exposed to study drug for <3 months and discontinue treatment before reaching the Day 365 Visit may have breast cancer surveillance imaging performed at the investigator's discretion.

Table 3: Schedule of Assessments for the Continued Long-Term Extension Period (Part C)

| | | | | | Continued | LTE Period | | | | | EOS/ Follow-Up |
|---|-----------------|-----------------|-----------------|-----------------|-----------------|-----------------|----------------------------------|-----------------|------------------|---|-------------------|
| Study Day/ Recurring Visit ^a | Day 365 (±5) | Day 449 (±7) | Day 533 (±7) | Day 617 (±7) | Day 701 (±7) | Day 785 (±7) | Day 869 (±7) | Day 953 (±7) | Day 1037 (±7) | Day 1121 (±7) | Day 1149 (±3) |
| | | | | | | | | | | End of Treatment /ET ^b | |
| Telephone call/in- home or in-person visit ^a | IP | IP | IP | IP | PC |
| Informed consent | Xc | | | | | | | | | | |
| Serum/urine pregnancy test (female subjects only) ^d | | ← | | | 505, 533, 561 | | 5, 673, 701, 7 065, 1093, and | | | | Х |
| Weight and BMI | | | X | | Х | | X | | X | X | |
| 12-Lead ECG ^e | | | X | | X | | X | | X | X | |
| Vital signs ^f | | | X | | X | | X | | X | X | |
| Physical exam ^g | | | X | | X | | X | | X | X | |
| Clinical laboratory tests ^h | | | X | | X | | X | | X | Х | |
| ALSFRS-Ri | | Х | X | Χ | Х | X | X | X | X | X | Х |
| ALSAQ-40 | | Х | Х | Х | Х | Х | Х | Х | X | Х | |
| C-SSRS ^j | | Х | Х | X | Х | X | Х | X | X | X | Х |
| Study drug dispensation | Х | Х | Х | Х | Х | Х | Х | Х | Х | | |
| Adverse events | | Х | Х | Х | Х | X | X | Х | X | X | Х |
| Prior/concomitant medications | | Х | Х | Х | Х | Х | Х | Х | Х | Х | Х |
| Mammogram ^k | Х | | | | Х | | | | | Xι | |

Abbreviations: ALSAQ-40, ALS Assessment Questionnaire; ALSFRS-R, ALS Functional Rating Scale-Revised; C-SSRS, Columbia-Suicide Severity Rating Scale; ECG, electrocardiogram; EOS, end of study; ET, early termination; IP, in-person; PC, telephone call; PI, Principal Investigator

^a All study visits during the Continued LTE Period should be conducted on-site. Visits indicated as in-person only may be conducted remotely (ie, in-home) following discussion between the site and the medical monitor. In-person visits that are conducted remotely must include the following assessments, at minimum (if such assessments are typically included during the visit): serum/urine pregnancy test (females only), vital signs, clinical laboratory tests, ALSFRS-R, C-SSRS, adverse events, prior/concomitant medications, and ALSAQ-40.

^b For subjects who early terminate from the study and consent to continued follow-up, the investigator should attempt to gain vital status on the participant and conduct the ALSFRS-R assessment approximately every 28 days for the remaining duration of the study, in accordance with local requirements/regulations.

^c Subjects who decide to enter the Continued LTE Period should sign the consent form before the start of the Continued LTE Period.

d Women of childbearing potential will undergo monthly urine pregnancy testing for the duration of the Continued LTE Period, and at the EOS/Follow-up visit or Early Termination. If a urine pregnancy test is positive, a serum pregnancy test will be conducted for confirmation and dosing should be immediately suspended and evaluated for continued study participation based upon the result of the serum pregnancy test and in discussion with the medical monitor. Subjects will complete a urine pregnancy test at home, if local requirements allow, to be reported to the investigator and documented in the eCRF.

PTC857-CNS-001-ALS

Clinical Protocol

- e Single 12-lead ECG measurements will always be performed prior to the dose of medication administered at the clinic. Subjects should be resting for at least 5 minutes in supine position prior to 12-lead ECG procedures.
- f Vital signs will consist of measurements of supine blood pressure, heart rate, body temperature, and respiratory rate. Vital sign measurements will be collected after the subject has been resting for 5 minutes. Blood pressure and heart rate measurements will be performed with subjects in a supine position, except when they are semi reclined because of study procedures and/or adverse events (eg, nausea, dizziness) or if deemed necessary by the PI or designee.
- ⁹ A targeted physical examination, including neurological examination, will be completed at all indicated timepoints.
- ^h Clinical laboratory tests will consist of hematology, coagulation, blood chemistry, and urinalysis.
- ¹ The ALSFRS-R assessment must be performed by a certified rater.
- At all visits, the Since Last Visits C-SSRS will be administered.
- ^k Mammograms to be conducted for female subjects only. If clinically indicated, an ultrasound or MRI may also be conducted for breast cancer imaging, per the investigator's discretion. ALS is a progressive disease, that over time causes severe disability. Thus, if the PI believes that continued breast cancer surveillance is no longer feasible for a specific patent, this test may be skipped, after discussion with the medical monitor.
- Women who discontinue from the study prior to the End of Treatment Visit may have breast cancer surveillance imaging performed at the Early Termination Visit, at the investigator's discretion.

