7.2.5. Clinical Laboratory Assessments

Blood samples will be taken under fasted conditions. Subjects will not be allowed to eat for a period of 8 hours prior to blood sampling or drink (except water) for a period of 4 hours prior to blood sampling.

All clinical laboratory tests listed in Table 5 will be performed as outlined in the Schedule of Assessments (Table 1 and Table 2). In addition, laboratory safety tests may be performed at various unscheduled timepoints if deemed necessary by the PI or designee.

Clinically significant laboratory abnormalities must be reported by the investigator as an AE or SAE as appropriate.

The results of all laboratory tests will be provided to the investigator in order for the investigation to make an assessment of clinical significance, with the exception of the lipid (cholesterol [total], low-density lipoprotein [LDL], high-density lipoprotein [HDL], triglycerides, apolipoprotein A, apolipoprotein B), amylase, and lipase values. The lipid, amylase, and lipase values (both individual subjects and study level) will be monitored regularly for the entirety of the study by the DSMB.

Table 5: Summary of Clinical Laboratory Tests

| Hematology | Chemistry | Urinalysis | Others |
|-------------------------|------------------------------------|------------------|----------------------|
| Hemoglobin | Urea | Urobilinogen | Serum/urine |
| Hematocrit | Creatinine | Nitrite | pregnancy test |
| RBC count | Fasting glucose | pН | (β-HCG) ^b |
| Reticulocytes | Sodium | Glucose | FSH |
| Platelet count | Potassium | Total protein | Coagulation (PT |
| WBC count | ALT | Erythrocytes | [sec], PT [INR], |
| Neutrophils | AST | Leukocytes | aPTT) |
| Eosinophils | GGT | Ketones | |
| Monocytes | Bilirubin (total, direct/indirect) | Microscopya | |
| Basophils | Alkaline phosphatase | Specific gravity | |
| Lymphocytes | Albumin | Bilirubin | |
| Mean corpuscular volume | Cholesterol (total) | | |
| | LDL | | |
| | HDL | | |
| | Triglycerides | | |
| | LDH | | |
| | Amylase | | |
| | Lipase | | |
| | Apolipoprotein A | | |
| | Apolipoprotein B | | |

Abbreviations: β-HCG, beta human chorionic gonadotropin; ALT, alanine aminotransferase; aPTT, activated partial thromboplastin time; AST, aspartate aminotransferase; FSH, follicle-stimulating hormone:

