7.3.15. Safety Oversight

An independent DSMB will be utilized during the study. The DSMB will closely monitor potential emerging safety signals in all subjects in the study throughout their study participation, including the planned transition without interruption in treatment from Part A to Part B of the study.

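### The DSMB is to monitor lipids for the whole study, but the Part C laboratory footnote drops the fasting lipid profile, while Table 5 implies it stays

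*Protocol*

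**What the plan says.** Section 7.2.5 of the protocol gives investigators all laboratory results "with the exception of the lipid (cholesterol [total], low-density lipoprotein [LDL], high-density lipoprotein [HDL], triglycerides, apolipoprotein A, apolipoprotein B), amylase, and lipase values". It says these withheld values "will be monitored regularly for the entirety of the study by the DSMB". Section 7.3.15 adds that the DSMB "will closely monitor potential emerging safety signals in all subjects in the study throughout their study participation".

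The schedules are less uniform. Table 1 footnote o (Part A) and Table 2 footnote m (Part B) name five components of the laboratory tests: fasting lipid profile, hematology, coagulation, blood chemistry and urinalysis. Table 3 footnote h (Part C) names four: "Clinical laboratory tests will consist of hematology, coagulation, blood chemistry, and urinalysis". The footnotes for Day 14 (Part A) and Day 183 (Part B) say that only the fasting lipid profile is taken and that blood chemistry is not evaluated.

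Table 5 lists total cholesterol, LDL, HDL, triglycerides and apolipoproteins A and B in its Chemistry column, beside amylase and lipase. Section 7.2.5 says that the Table 5 tests "will be performed as outlined in the Schedule of Assessments (Table 1 and Table 2"), without mention of Table 3.

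In Section 6.4 of the Part B/C SAP, the lipid row's last numbered visit is Day 365, followed by ET. The chemistry row continues to Days 533, 701, 869 and 1037, then ET.

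**The concern.** Because investigators do not see lipid results, routine review of them rests on the DSMB. If no lipids are drawn in Part C, the DSMB cannot do what Section 7.2.5 says it will do. Section 7.2.5 does state that "laboratory safety tests may be performed at various unscheduled timepoints if deemed necessary by the PI or designee", but an investigator has no lipid result that could prompt such a test.

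Section 1.5.3 lists lipoprotein changes as the only potential risk recognized so far. Section 1.5.1 reports lipid changes in healthy volunteers after short exposure, and Section 1.4.2 gives 14 days as the longest treatment in completed studies. Part C is most of the planned time on drug, so the question is whether the one listed potential risk is followed during that time. Efficacy results and the Part C endpoints are not affected.

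**Working it through.** The plan gives no figure of its own here. The check compares the texts and counts visits.

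**Is the lipid profile part of blood chemistry?**
- Table 1 footnote o and Table 2 footnote m list the two as separate items.
- The Day 14 and Day 183 footnotes take lipids while stating that blood chemistry is not evaluated. They make sense only if the two are separate.
- The Part B/C SAP keeps separate rows with different visits.
- Table 5 alone puts lipids under Chemistry, and Section 7.2.5 ties Table 5 to Tables 1 and 2 only. The missing reference to Table 3 may simply be out of date.

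If lipids are separate, footnote h leaves them out of Part C and the whole-study commitment fails. If they are chemistry, the commitment can be met, but the Day 14 and Day 183 footnotes contradict themselves.

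**Amylase and lipase.** They appear only under Chemistry, which Part C keeps, so they are collected on either reading. The conflict is limited to lipids.

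**Part C visits** (Table 3: start Day 365, laboratory visits Days 533, 701, 869, 1037 and 1121)
- Length: (1121 − 365)/7 = 108 weeks.
- Laboratory visits at 24, 48, 72, 96 and 108 weeks after Day 365, so gaps of 24, 24, 24, 24 and 12 weeks.

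| Text that governs | Part C lipid draws |
|---|---|
| Table 5 | 5 (longest gap 24 weeks) |
| Footnote h | 0 |
| Part B/C SAP lipid row | 0, or 1 if ET means the Day 1121 visit |

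**Time on drug and earlier lipid draws**

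| | Started on PTC857 | Started on placebo |
|---|---|---|
| Planned weeks on PTC857 | (1121 − 1)/7 = 160 | (1121 − 169)/7 = 136 |
| Part C share | 108/160 = 67.5% | 108/136 = 79.4% |
| Weeks on drug at Day 365 | (365 − 1)/7 = 52 | (365 − 169)/7 = 28 |
| On-drug lipid draws up to Day 365 | 10 (Days 14, 29, 57, 85, 169, 183, 197, 225, 253, 365) | 5 (Days 183, 197, 225, 253, 365) |

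**The case against.** The best defence is that Table 5 is the only place where the protocol itemizes its panels. Lipids stand there under Chemistry, so footnote h's blood chemistry would include them, and the earlier footnotes would merely name a subset that is drawn alone at Days 14 and 183. A laboratory could reasonably read it that way. That makes the outcome in Part C uncertain, but it does not reconcile the texts, because the Day 14 and Day 183 footnotes exclude blood chemistry from visits at which lipids are drawn.

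The SAP row is weak evidence on its own. It does not set collection, it puts LDH with the lipids, and it omits the apolipoproteins. The SAP's general text would summarize whatever laboratory parameters are collected. This is accepted, and the conflict stands on the protocol alone.

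Stopping lipids at Day 365 could also be deliberate. Part C is a reduced schedule. Subjects enter it after 28 or 52 weeks of scheduled on-drug lipid monitoring. The protocol calls the short-term changes reversible, reports none in monkeys and states that there are no important risks. That would be a defensible choice, but it is not stated and it does not fit a whole-study commitment.

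A DSMB charter or the Investigator's Brochure may contain further provisions. Neither is among the documents, and clinical events could still prompt an unscheduled test. These points keep the matter at the level of a recommended correction. They do not remove it.

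**Conclusion.** The concern holds. The commitment to whole-study DSMB lipid monitoring, footnote h, the Day 14 and Day 183 footnotes and Table 5 cannot all be followed. Depending on which governs, Part C yields five lipid draws or none per completer, with at most one on the SAP row. Following footnote h as written leaves the DSMB without scheduled lipid data for 108 weeks. That is 67.5% of planned time on drug for subjects who started on PTC857 and 79.4% for those who started on placebo.

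These shares are for completers. Part C is optional, and no attrition is assumed, so they are upper limits for subjects who leave early. The consequence is confined to safety oversight of lipids.

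**What to change.** Add the fasting lipid profile to Table 3 footnote h at the existing laboratory visits (Days 533, 701, 869, 1037 and 1121). Cite Table 3 in Section 7.2.5 beside Tables 1 and 2, and extend the lipid row in Section 6.4 of the Part B/C SAP to the same visits.

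If lipid testing is meant to end at Day 365, limit the lipid part of the DSMB statement in Section 7.2.5 to Parts A and B and give the reason.

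Amylase and lipase need no protocol change. Listing them and the apolipoproteins in the SAP table would be optional tidying.

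The cost is a small assay charge at five visits where blood is already drawn, plus one footnote, one cross-reference and one SAP row. No new visit or fasting requirement is needed, since Section 7.2.5 already states: "Blood samples will be taken under fasted conditions".

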3.3. Number of Subjects

The study is targeted to have approximately 307 subjects in the ITT1 Analysis Set (205 in the PTC857 group and 102 in the placebo group, based on a 2:1 randomization ratio).

Approximately 36 subjects from select sites participating in the PK Sub-Study will participate in serial blood sampling to characterize the PK of PTC857 in subjects with ALS.

